8.7.16 Questions 16 and 16a

If the candidate is not in an intensive weight loss program, mark the bubble “No”, do not answer 16a, but proceed to question 17. **Long-term weight loss maintenance programs, such as Weight Watchers, Take Off Pounds Sensibly (TOPS), or Overeaters Anonymous (OA) are not considered “active” weight loss programs and do not exclude the candidate.** If the candidate is in one of these or similar long term weight loss maintenance programs you should mark “No” to this question and proceed to question 17.

If the candidate is enrolled in an intensive weight loss program mark the “Yes” bubble and go to question 16a. If the candidate is enrolled in a short-term, active or intensive weight loss program, it will be impossible to evaluate the effects of PRIDE’s weight loss intervention. Therefore, candidates must be willing to stop any current intensive weight loss program in order to qualify for PRIDE.

It is important to ascertain whether the candidate is in a weight loss program that is prescribed and monitored by a health care provider. In this case, even if she is willing to stop, she must obtain a letter of agreement from that health care provider that she can stop her current program for approximately 22 months. In such cases, continue screening but note on the Participant Tracking Log that a “clearance to participate” letter must be obtained prior to Randomization. Tell the candidate you will mail her some information and a form for her health care provider to sign and fax to the PRIDE site.

If the candidate is enrolled in a self-initiated active weight loss program and is willing to stop, she can continue screening. However, a note should be made on the log sheet to confirm during the Screening Visits that the weight loss program has been discontinued.

As mentioned earlier, the investigator may choose to avoid screening women who have participated in intensive weight loss programs at her/his clinical site within the past 5 years since the intervention materials will be too similar. Please document the number of candidates who are not suitable study candidates due to previous participation in local intensive weight loss programs and provide these numbers to the Coordinating Center at the end of enrollment.

8.7.17 Question 17

This question refers to **prescription medications** only. If the candidate is not taking any prescription medications for urinary incontinence or for weight loss then mark the bubble “No” and go to question 18.

If the response is “Yes”, go to question 17a.

8.7.18 Question 17a

Ask the candidate to tell you the name of any prescription medication she is taking and compare that with the list of exclusionary medications in 17a and in Additional Medication List, Appendix 8C. (The Additional Medication list has been designed to capture new medications that have been approved since PRIDE started.) **Fill in the bubble “Yes” or “No” for each medication.** If the medication(s) is listed in Appendix 8C, please mark “yes” for item 17aV and indicate the code number of the medication(s) in the field(s) provided. If the medications marked with an asterisk are prescribed for depression rather than incontinence, then fill in the bubble “No” beside that medication. If the participant can’t remember the names of her medications and doesn’t have them handy read the list to her to her and mark “Yes” or “No” for each medication on the list. Proceed to question 17b. Please note that if you fail to mark “Yes” or “No” for each medication a query will be generated.

If all the medications are marked “No”, ask the candidate to read the name of her prescription medication if possible and , double check the lists. If the medication is not on either list, make a correction to the form by crossing out the “Yes” response to question 17, marking the “No” response and circling it, and drawing a diagonal line across the list of medications. Initial and date the correction. Go on to question 18.

Please note – If a participant is taking a new exclusionary medication for incontinence, weight loss, diabetes, or a new steroid, please notify the Coordinating Center and request that the Additional Medications List be updated accordingly.

8.7.19 Question 17b

If the candidate is willing to stop her prescription medication she must first call the prescribing physician, obtain a letter of agreement and discontinue the

medication under the physician's guidance. If the candidate is willing to do this, offer to mail her information and a form for the physician to sign and fax to the PRIDE site. Make a note on the Participant Tracking Log that the medication must be discontinued and a letter received from the health care provider by the time of the randomization visit.

If the candidate is not willing to stop the prescription medication that she is taking for weight loss or incontinence she is not eligible for PRIDE. Fill in the bubble "No" and skip to question 30.

8.7.20 Questions 18 and 18a

The PRIDE staff cannot provide primary medical care for the candidate. If the candidate does not have a primary health care provider (fill in the bubble "No" to question 18) but is willing to find one (fill in the bubble "Yes" for question 18a) you may continue screening. Make a note on the tracking log that this issue should be resolved prior to the Randomization Visit. You may help by providing names from a list of local Primary Care Physicians who are willing to take referrals. If the candidate does not want to initiate contact with a physician, she is not eligible for PRIDE. In this case, fill in the bubble "No" for question 18a and skip to question 30.

8.7.21 Question 19a - d

Read question 19 to the candidate and then read each of the medical conditions/procedures in questions 19a, 19b, 19c and 19d. Fill in the bubble "yes" or "no" for each item. If any of the responses is "yes", the candidate is not eligible for the study and you should skip to question 30.

19a and 19b. Cancer of the pelvis, including uterine, ovarian, vaginal or cervical cancer exclude the candidate from the study even if this condition has been treated successfully with radiation or with medical therapy. Women who have had cervical or vaginal dysplasia (non-invasive cervical neoplasm) are eligible to continue screening.

19c. Urethral surgery is surgery on the urethra, the tube that carries urine from the bladder to the outside. This may be done to relieve an obstruction, repair a defect (urethral diverticulum) or to treat incontinence. Women who have had urethral dilation which was NOT done specifically for the purpose of treating or improving urinary incontinence are eligible to continue screening.

19d. The following surgeries for urinary incontinence exclude the candidate: needle urethropexy (Peyera, Stamey, or Raz), retropubic procedures (Burch, Marshall-Marchetti-Krantz, or Tanago colposuspension procedure), sling procedures, tension-free vaginal tape (TVT), intra-vesical therapy (botox), and/or urethral bulk injections (Durasphere, collagen). Women who have had anterior repair or cystocele repair which was NOT done specifically for the purpose of treating or improving urinary incontinence are eligible to continue screening. If there are questions about whether specific types of surgery exclude a participant, call the Coordinating Center for advice.

"Bladder raised" is a common description for a procedure done for incontinence; it is also a layman's term for an anterior vaginal repair that was once thought to improve incontinence but now is proven not to be effective. If a candidate reports having had her "bladder raised" she is NOT eligible for PRIDE, unless she can provide additional information on the surgery. If she had a vaginal hysterectomy and repair of her vagina (anterior repair, anterior colporrhaphy) without a sling or other suspension, she is eligible. (It is very common for a woman to have a vaginal hysterectomy with repair of the vagina – her gynecologist will tell her the surgery will lift her bladder, which is true, but this is not an effective surgery for incontinence).

8.7.22 Question 20a - d

Read question 20 to the candidate and then read each of the medical conditions/procedures in questions 20a, 20b, 20c and 20d. Fill in the bubble "yes" or "no" for each item. If the candidate reports "chest pain" or "difficulty breathing" ask if she has seen a doctor for her symptoms. Probe to determine the correct diagnosis. If this is unclear, consult the Principal Investigator or Coordinating Center for direction. If any of the responses are marked "yes", continue to question 20e.

8.7.23 Question 20e

Candidates with coronary heart disease must have permission from a cardiologist or primary care physician to participate in PRIDE. Even though the exercise program is not considered strenuous, the candidate may have been sedentary for a long time and caution is prudent. Ask the candidate if she is willing to obtain written approval from a medical professional to participate in the study. If she says "yes", she is eligible to continue screening. You can offer to send study information and a form for her doctor to sign and fax to the

PRIDE site. Make a note on the tracking log that a letter is expected prior to Randomization. Candidates currently enrolled in Cardiac Rehabilitation programs must finish these before being screened for PRIDE. Continue to question 21.

8.7.24 Question 21

If the candidate is a diabetic fill in the bubble “yes” for question 21 and proceed to answer question 21 a, and, if applicable, question 21 b and/or 21c. If the candidate is not a diabetic or doesn’t know, fill in the appropriate bubble and skip to question 22.

Please note: if the response to question 21a is “Don’t Know” be sure to flag the candidate for further follow-up. Insulin-dependent diabetics and diabetics on some oral medications are not eligible for the study. The method of treating their diabetes must be clarified before randomization can occur.

8.7.25 Questions 21a - c

Women who consider themselves to be diabetic but have been told they don’t need treatment or don’t know if they are treated for diabetes are eligible to continue screening. Fill in the bubble “No treatment” or “Don’t Know” and skip to question 22.

For question 21a, you must indicate all the responses that apply to the candidate. For instance, she may be on a calorie-restricted diet as well as taking oral medication for her diabetes. If so, fill in both these bubbles.

If the candidate is taking oral medication, fill in the appropriate bubble, then ask question 21b and read the list of medications. Fill in the bubble “Yes” or “No” for each of the drugs listed. If “Yes” is marked for any of the categories listed, the candidate is not eligible and you should skip to question 30. If the response is “No” to all of the medications listed, ask the candidate to tell you which medication she is taking. Make sure this is not a variation of one listed. Other oral anti-diabetic agents are allowed. Proceed with screening.

If the candidate is insulin-dependent, please fill in the appropriate bubble and ask question 21c. All current insulin products are listed on the Eligibility Form, thus the response to this question should be “Yes”. Fill in the bubble “Yes” and skip to question 30. If the candidate answers “No” or “Don’t Know” she may be confused, and this issue must be resolved when she brings all her

medications to a clinic visit. Mark the appropriate bubble and continue to question 22.

8.7.26 Question 22

Candidates who have not had cancer or don't know if they have had cancer **in the past 5 years** are eligible to continue screening. Mark the appropriate bubble and skip to question 23.

If the candidate has had cancer (except non-melanoma skin cancer) **in the past 5 years** fill in the "Yes" bubble and answer questions 22a – 22c.

NOTE: candidates with prior urogenital cancer (uterine, ovarian, vaginal or cervical cancer) at any time in the past would be excluded from study participation in question 19.

8.7.27 Questions 22a - c

Cancers that exclude the candidate, regardless of when the cancer occurred, are: uterine, ovarian, vaginal or cervical cancer. Women who have had cervical or vaginal dysplasia or Squamous Intraepithelial Lesion (SIL) (non-invasive cervical neoplasm), are eligible to continue screening.

For cancers that are not in the urogenital tract, the candidate must be cancer-free for at least 5 years.

8.7.28 Question 23

Medical conditions such as AIDS or HIV compromise the immune system and may directly or indirectly lead to problems or medications that confound the study results. Therefore, if the response to this question is "Yes", the candidate is not eligible and you should skip to question 30. If you are concerned that the candidate may find this particular question discriminatory, you may continue with the remainder of the screening questions and be non-specific about the reason for lack of eligibility.

8.7.29 Questions 24 and 25

If a candidate is unable to walk 2 blocks without stopping or needs a cane or walker, she is unlikely to be able to engage in the prescribed exercise program

and is not eligible for the study.

8.7.30 Question 26

A candidate is not eligible for the study if she is planning to move to a location that makes it impossible to attend study lessons or visits. A move that is closer to the PRIDE site or has no impact on study participation should be marked as a “No” response.

8.7.31 Question 27

While planned travel is not an exclusionary criterion, it may impact the candidate’s ability to attend the intervention sessions or the study visits. Make a brief note in the boxes provided on the form (for example, “FREQUENT TRAVELER”) and notify the Study Coordinator or Principal Investigator prior to the Orientation Visit.

8.7.32 Questions 28 and 28a - b

If the candidate is not enrolled in any other type of research project fill in the “No” bubble and continue to question 29. If the response is “Yes”, fill in the “Yes” bubble and answer questions 28a and 28b. Most research studies involving active interventions prohibit candidates from enrolling concurrently in another trial. If the candidate is taking a study-prescribed medication or following a study-prescribed behavioral change program such as diet or exercise, she is not eligible for PRIDE. If she is enrolled in a long-term non-interventional study (for example, an observational trial such as the Nurses’ Health Study), she is eligible for PRIDE. Please confirm eligibility by discussing this situation with the Principal Investigator.

8.7.33 Question 29

Ask how the candidate heard about PRIDE and mark all responses that apply.

8.7.34 Question 30

Choose the ONE response that best suits the candidate’s eligibility status at this time.

- If the candidate is eligible and willing, mark the “**Eligible**” bubble

and make an appointment for the candidate to attend the first available Orientation session.

- If you have skipped to question 30 because the candidate is not eligible for PRIDE please mark the “**Not Eligible**” bubble and enter the number of the question on the Eligibility form that led you to conclude the candidate should be excluded. If this is a sub-category to a question you must enter the sub-category letter also (for example 22c or 28b). Please see section 8.8 for instructions about re-screening candidates.
- If the candidate appeared to be eligible but was unsure about her commitment, has to wait for a day or a nighttime cohort, had to check with a doctor and was unsure about her/his approval, etc. then fill in the bubble “**Pending**” and schedule a time to call her back for resolution. The eligibility form should be faxed to the Coordinating Center at this time. When the issue that is pending is resolved, the Study Coordinator should post a query on the Website and make a correction to question 30, changing the Eligibility Status to the appropriate final status of the candidate. If you select “pending” please be consistent with the way you express the reasons. For example, please enter “Day Group” or “Night Group” as appropriate, if the candidate is to be held for the next session. Reminder: If the interval between the Eligibility Screening and the Orientation session is more than 3 months, then all questions on the Eligibility Screening form must be reviewed with the participant before proceeding with Orientation. Post queries as necessary to correct information that has changed.
- If the candidate is eligible but is **unwilling to participate**, mark the last bubble, thank her very much for her time and encourage her to call back if she should change her mind.

8.8 RE-SCREENING

You may re-screen a candidate at a later time if she fails to meet entry criteria that may or will change (for example, age, pregnancy status, participating in an intervention trial that is ending soon, insufficient incontinence episodes etc.). When a candidate is re-screened she must be assigned a new, unique ID number and an entire new set of data forms must be completed. The new ID number should be recorded on the Participant Tracking log along with the original ID number. At the end of the recruitment period the study coordinator should provide a list to the Coordinating Center of all candidates who have been re-screened, identifying all ID numbers used

for the same person.

8.8.1 Re-Screening Due to Change in BMI Entry Criterion

In July, 2005 the PRIDE DSMB approved a proposal from the PRIDE Steering Committee to expand the Body Mass Index entry range from 25 – 45 kg/m² to 25 – 50 kg/m². Several women who did not meet entry criteria during the initial telephone interview or when they were first weighed at the clinic may be re-screened now.

In ALL cases where you are re-screening due to expanded BMI criteria, please assign a new ID number and start all over as though this were a new participant. Be sure to indicate in the participant tracking log that this participant is a re-screen. Assign a new number, print new, updated data forms and complete all forms and procedures as you would for any new candidate, regardless of the length of time that has elapsed since the woman was first screened.

Please remember that you should not be conducting any screening according to the new criteria until Protocol Amendment #3 has been approved by your IRB.

8.9 SCREENING SCENARIOS

Once an eligibility form has been sent to the Coordinating Center for an eligible candidate, the status of that candidate must be tracked and documented. Appendix 8B is a summary of various situations that may occur during screening with an indication of the forms to be used to document each.

APPENDIX 8A

PRIDE TELEPHONE SAMPLE SCREENING INTERVIEW SCRIPT

Interviewer note: if you are the individual placing or returning a call and are not able to speak to the potential participant, just say that you will call at another time. Do not give details of the study to another person in the household. Respect the confidentiality of the respondent – she may not want anyone to know she is thinking about participating in a study about incontinence or weight loss.

Hello, my name is _____.

May I please speak to _____?]

I'm calling from the _____ [say name of institution] _____ in response to your interest in the PRIDE study.

Do you have a few minutes to talk now?

Yes

No - When may I call back?

[figure not shown]
First, I would like to tell you a little about the study. Urinary incontinence or involuntary leaking of urine is a condition that affects thousands of women, in particular women who are overweight. This is a study to determine whether losing weight can help relieve the symptoms of urinary incontinence. The study lasts 18 months. It involves several group classes led by behavioral experts to promote weight loss by diet and exercise; and we provide information about exercises that can help control incontinence. There will be questionnaires that you can fill out at home and measurements taken at our clinic to see if there are changes in weight and changes in the number of times you leak urine. Are you interested in answering some questions to see if you would be an eligible candidate for the study?

Yes – proceed with interview

No

Thank you for your time. If you should change your mind, please feel free to call us at () _____.

Appendix 8B

NOTE: During screening, on the Inclusion/Exclusion form, mark **only one** most important reason why candidate is not eligible. **Leave all other reasons blank.**

**APPENDIX 8C
ADDITIONAL EXCLUSIONARY MEDICATIONS LIST**

Use of the following medications at baseline excludes the participant from participating in PRIDE:

No.	Brand	Generic	Classification
01.	Enablex	darifenacin	Incontinence
02.	Levsinex Timecaps	hycoscymine	Incontinence
03.	Sanctura	tospium	Incontinence
04.	VESIcare	solifenacin	Incontinence
05.	Decadron	dexamethasone	Steroids
06.	Cortone	cortisone	Steroids
07.	Orapred, Pediapred, Prelone	prednisolone	Steroids
08.	Sterapred, Sterapred DS		Steroids
09.	Tenuate, Tenuate dospan	diethylpropion	Weight Loss
10.	Adipex-P	phentermine	Weight Loss

CHAPTER 9

ORIENTATION VISIT

9.0 ORIENTATION VISIT

9.1 OVERVIEW

Orientation Visits (OV) are group visits to which eligible respondents are invited after the Eligibility Screening interview. This visit can be useful to:

- efficiently explain the study purpose and requirements and create enthusiasm for the study
- provide an opportunity for attendees to experience motivational aspects of the “group” encounter
- assess the likelihood of participant adherence to a lesson or visit schedule

9.2 OV VISIT SCHEDULE

The site will schedule, in advance, a series of Orientation Visits so that an interviewer will be able to offer dates, times and locations to candidates who are eligible and willing after the Eligibility Screening interview. Optimally, some evening or weekend sessions should be available. A confirmation letter and directions will be mailed to the candidate at least one week in advance of the OV. Include in the letter a reminder to bring glasses if needed for reading or for viewing the slide presentation.

9.3 ORIENTATION PROCEDURES

Forms/Logs Needed for this Visit:

- Screening Visit Checklist
- Brief or Full Informed Consent/HIPPA Authorization
- 7-day Voiding Diary #1
- 2IQ (on-site or take-home)
- Demographics (on-site or take-home)
- Contact Information (local form)
- Physician Consent Forms (local form)
- Participant Tracking Log

The investigator or designated staff will explain the purpose of the study (using the slideshow if you wish) and will describe the intervention, the random group assignments, the study schedule and the informed consent document. It may be helpful to let participants know that, if they qualify and participate, they will receive attention

from experts in weight loss and incontinence. Questions should be invited from the audience, and general eligibility and interest level assessed.

Informed consent will be obtained at this time. At the discretion of the investigator, consent can be either a brief consent to fill out a 7-day voiding diary or the main study Informed Consent.

At the end of the Orientation, the participant will be asked to fill out the 2IQ form (see Chapter 9.3.2), or to complete it at home and bring it back to SV1. The Study Coordinator or designated staff person will meet individually with each attendee to explain in detail the 7-day Voiding Diary which the participant will complete at home prior to SV1 (please see Chapter 9.3.3).

9.3.1 Informed Consent and Health Information Portability and Accountability Act (HIPAA) Compliance

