8.4.3. Incontinence questionnaire. The incontinence questionnaire is a self-report measure of incontinence severity. It includes the 2 Incontinence Questions (2IQ), American Urological Association Symptom Index (AUA Symptom Index), Sandvik Severity Index, and Incontinence Expense Questionnaire. The 2IQ is a short questionnaire to diagnose the type of urinary incontinence in women. It is currently being studied in a multi-site study to compare the accuracy of the 2 -IQ compared to a standard extended evaluation for diagnosis of incontinence type (Diagnostic Aspects of Incontinence Study; Coordinating Center PI: [name]). We have added a third question to assess bothersomeness of each type of incontinence. The AUA Symptom Index and the Sandvik Severity Index are validated instruments to assess lower urinary tract and incontinence symptoms, respectively. For the Incontinence Expense Questionnaire, participants record resources used in an average week specifically for incontinence (pads, protection, laundry, dry cleaning). A generalizable cost for the resources is then estimated by multiplying resources used by national resource cost estimates.

8.4.4. Sexual function questionnaire. The sexual function questionnaire is a self-report survey of sexual activity, satisfaction with sexual activity and four sexual function domains (interest, ability to relax, arousal and orgasm).

8.4.5. Bowel habits questionnaire. The Bowel Habits Questionnaire is a self-report survey to assess bowel function and habits, including frequency, consistency, straining with bowel movements, constipation, fecal and flatal incontinence. The questionnaire was developed from often-used instruments, including the ROME II criteria, Gastrointestinal Quality of Life Index, and **scoring system for the assessment of bowel and lower urinary tract symptoms in women.** The Bowel habits Questionnaire in PRIDE underwent extensive pretesting and is currently being validated in the Reproductive Risks for Incontinence Study at Kaiser (RRISK).

8.4.6. Weight, height and body mass index Weight will be recorded in kilograms using a calibrated scale. Participants will be measured in light clothing

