9.3.2 The Two Incontinence Questionnaire (2IQ)

This is a one page, 2-item, self-administered questionnaire designed to diagnose the type of urinary incontinence experienced by the participant. The accuracy of this brief questionnaire is being tested versus extensive medical assessments in a concurrent urinary incontinence trial. This questionnaire should be completed early in the study before the participant receives any training or information about incontinence.

The introductory, unnumbered question checks that the participant has leaked some urine in the last 3 months. If the response is "No" the participant is not eligible for the study and the coordinator should review the Eligibility Screening form to check for erroneous information about current incontinence.

Questions #1 and #2 can have multiple responses. Participants are asked to fill in all bubbles that apply. When this is completed the form should be reviewed at the clinic and faxed to the Coordinating Center data system.

9.3.3 7-Day Voiding Diary

The 7-day Voiding Diary will be collected once during Screening to determine eligibility, then again at the Randomization Visit, and at Months 6, 12 and 18. This diary is a primary outcome measurement for PRIDE and it is extremely important that the participant understands how to fill out the diary.

Two versions of the voiding diary are available – a short and a long version. The long version should be given to all participants initially. It allows for the

recording of up to 40 episodes of urinary incontinence daily and has one extra page at the back. The shorter version allows for the recording of up to 18 episodes daily and has two extra pages at the back. The short version may be used when the initial diary has been reviewed and it seems unlikely that the participant will need space provided by the long version.

Every effort should be made by study staff to encourage participants to fully complete all diary information and bring the diary to the next visit. Suggest that the participant carry the diary with her every day for seven days. If she is unable to do this suggest that she record her episodes on a piece of paper and transcribe them at the end of the day.

Staff will hand write Subject ID # and acrostic on *every* diary day page. Use the instructions on the inside cover of the diary to explain, in detail, diary entry procedures to the participant. For 7 days, she should record every time she urinates in the toilet and leaks urine.

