Using a calendar, mark the scheduled date of the participant's Screening Visit 1 and arrange a mutually agreeable start date for the diary, keeping in mind that she must start it at least 8 days prior to the next study visit. We recommend that the participant start the diary *the morning after* she receives it. If this is not feasible discuss with the participant an alternate day to start the diary. Ideally she will fill the diary out daily for 7 consecutive days and bring it back to the next visit. If she forgets a day, instruct her to continue recording beginning the day after the one she forgot and to finish 7 complete days.

Written instructions for how to fill out the diary are included at the beginning of the diary and in Appendix 9A. Appendix 9A includes a sample reminder letter for participants also. Ask the participant to strike through "Page 2" any time she does not need these extra spaces. This will make it easier for you and she to review the diary later.

Review the symptoms of "Urge" vs "Stress" incontinence with the participant. Tell her to mark "Other" only if her leaking episode doesn't seem to fit either Urge or Stress. Ask her to describe very briefly in column 4, what she was doing when she leaked urine, especially if she marks "Other". She does not have to write in column 4 if she urinates in the toilet without leaking. Explain that you will review her diary with her when she returns. Tell the participant that she can call the Study Coordinator to ask questions while completing the voiding diary. When you are finished explaining the diary:

- determine if the participant has any questions about how to complete the diary
- provide a couple of hypothetical scenarios and ask her to tell you how she would record these in the diary
- remind the participant to bring the completed diary with her to the next visit
- if she can't start the diary the next morning, make a note of when she plans to start and call her the day before to remind her that she is to start the diary the next day

Occasionally, it can be a challenge for the participant to identify the type of incontinence episode she has experienced. Here are some examples that may be helpful:

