9.4 SCHEDULING SV1

At the end of the OV, a Screening Visit 1 should be scheduled to take place at least 8 days after the Orientation Visit (to allow time to complete the 7-day Voiding Diary) but no longer than 9 months from the Eligibility Screening (ES) date (see Ch.9.4.1).

The participant should leave the Orientation with the following packet of forms to fill out at home:

- Contact Information/Physician Forms (local)
- Demographics Form (if not completed in clinic)
- 2IQ (if not completed in clinic)
- 7-day Voiding Diary

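### The manual says the 2IQ should come before any incontinence training, yet lets women complete it at home after staff have taught urge versus stress at the same visit

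*Protocol*

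**What the plan says.** **Timing.** Operations Manual 9.3.2 describes the 2IQ as a one-page, two-item, self-administered form for typing incontinence and gives it a place in the sequence: "This questionnaire should be completed early in the study before the participant receives any training or information about incontinence".

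**Take-home option.** Section 9.3 asks the woman to fill it in at the end of the Orientation Visit "or to complete it at home and bring it back to SV1". Section 9.4 lists it in the packet she takes home, next to the voiding diary, if she has not done it in the clinic. Section 10.3.2.1 has staff collect and check it at Screening Visit 1 (SV1) as a take-home questionnaire.

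**Teaching at the same visit.** Under 9.3, staff "meet individually with each attendee to explain in detail the 7-day Voiding Diary". Section 9.3.3 sets out what that involves: "Review the symptoms of 'Urge' vs 'Stress' incontinence with the participant", followed by hypothetical scenarios that she is asked to record. The section also supplies worked examples for leaks that are hard to classify. The diary's printed instructions (Appendix 9A) define urge and stress leakage.

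**Use of type.** Study Protocol 8.4.3 states: "The 2IQ is a short questionnaire to diagnose the type of urinary incontinence in women". Aim 3 (12.2.3) names incontinence type as a subgroup variable and plans subgroup-by-treatment interaction tests. Section 7.1.1 of the urodynamic substudy protocol checks the balance of type after the first 30 women.

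**The concern.** The form is meant to capture how an uninstructed woman describes her leakage. The manual allows it to be answered after one-to-one instruction on exactly the distinction it asks about, with the written definitions to hand. Other women may answer it on site before that instruction. One baseline variable then mixes answers given under two conditions, and the manual leaves to the site which condition applies to a given woman.

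If that variable defines the type subgroups, women with the same symptoms could be typed differently according to when they filled in the form. Such error would blur a comparison of treatment effects between types. If the two centers handle the form differently, it could also make the distribution of types look different between them.

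**Working it through.** No arithmetic applies, because the documents state no figure on this point. The check is to follow the routes the manual permits and ask whether each keeps the order stated in 9.3.2. Study Protocol 8.4.3 counts the 2IQ within the Incontinence Questionnaire, which the 8.1 schedule places at Screening Visit 2; I take the manual's own placement (Appendix 4A: Orientation Visit or SV1) as operative.

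1. **Orientation Visit, completed on site.** Section 9.3 mentions the 2IQ before the individual diary meeting but does not fix that order. The rule is met only if the form is done before the meeting.
2. **Orientation Visit, taken home.** The diary meeting, with its urge and stress review, takes place before she leaves. SV1 is at least 8 days later (9.4), and 9.3.3 recommends starting the diary the morning after it is received. She may therefore already be classifying her own leaks when she answers. The rule cannot be met on this route.
3. **No Orientation Visit.** The visit is optional (4.3.1). Appendix 4A allows the 2IQ at SV1, where 10.3.1 has the first diary handed out if it was not given before. Nothing says which comes first, so the rule may or may not be met.
4. **Orientation Visit attended, 2IQ first done at SV1.** Appendix 4A does not exclude this. It would come after the diary teaching and, typically, after the diary itself. The rule is not met.

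Route 2 alone establishes the conflict, since 9.3, 9.4 and 10.3.2.1 all provide for it.

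Next, does it reach an analysis? Section 12.2.3 lists type as a subgroup variable without naming an instrument. Section 8.4.1 shows that the voiding diary also classifies each episode as urge, stress or other. Section 7.1.1 of the substudy protocol sets two type categories, again without naming the source. The link from the 2IQ to Aim 3 or to the balance check is therefore possible but not stated.

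Finally, can it differ by arm? On every route the form comes before the Randomization Visit, so neither the woman nor the staff know her assignment. Differences between sites are possible; differences between arms are not expected.

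To put a size on the effect, one would need the share of women who take the form home, the share whose answer changes after instruction, and the direction of that change. None of the three is in the documents.

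**The case against.** The strongest reply has four parts.

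- **The rule is advisory.** Section 9.3.2 says should, not must, and does not declare a later 2IQ invalid. This stands. The conflict is between a stated recommendation and a procedure that defeats it.
- **Aim 3 may not use the 2IQ.** If type comes from the diary, every woman is typed after the same instruction and the subgroup variable is uniform. The choice of instrument may properly sit in an analysis plan that is not at hand. This stands too. A reader might infer that the Aim 3 subgroup is in fact measured before training in some women and after it in others; no section says so.
- **The loss cannot be sized.** A reader might infer a definite loss of power for the type-by-treatment interaction. The Aim 3 power statements concern treatment effects within subgroups of 50, 40 or 30% of the sample, and no power is given for an interaction. Aim 3 names three types, so a calculation with two equal groups would not describe it. Any misclassification rate would be invented, and instruction could make answers more accurate as easily as less.
- **SV1 has to be allowed.** Women who skip the Orientation Visit have no earlier occasion and have had no diary week beforehand. This stands, so SV1 should be kept for them with the order stated.

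None of this removes the contradiction within Chapter 9. A form sent home after the diary meeting cannot precede that meeting.

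**Conclusion.** The inconsistency is real and follows from the text alone: 9.3, 9.4 and 10.3.2.1 provide for a take-home 2IQ that necessarily comes after the teaching which 9.3.2 says it should precede. Women can therefore answer under different conditions according to site convenience.

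The consequence is conditional and limited. It matters for Aim 3 or the urodynamic balance check only if type is taken from the 2IQ. In that case it can add misclassification that may vary by site but should not vary by arm. Aims 1 and 2 are not affected. The size cannot be derived from the documents. The point is worth correcting because the form is short and the remedy is nearly free, not because a measurable loss has been shown.

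**What to change.** - **9.3 and 9.4:** delete the take-home option. State that the 2IQ is completed and collected on site, after consent and before the voiding diary is explained.
- **4.3.1 and 10.3.2.1:** align both with that order, and remove the 2IQ from the take-home forms collected at SV1.
- **Appendix 4A:** it contains no take-home option to delete, only permission for either visit. Restrict SV1 to women who did not complete the 2IQ at an Orientation Visit, and require it there before the diary is explained or handed out. The SV1 forms list in 10.3.1, which omits the 2IQ, should then include it for this case.
- **Consent:** 9.3 allows a brief consent for the diary alone. Where a site uses it, confirm that it also covers the 2IQ.

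It would also help to state which instrument defines incontinence type for Aim 3 and for the substudy check, here or in the analysis plan.

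The cost is a few minutes at the visit for a one-page form and an edit to the manual. No staff or procedure is added. If a site's brief consent does not cover the 2IQ, a wording change there would need local review board approval.
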